4.7. Prior Anti-cancer Therapy

The number and percentage of subjects who received prior systemic therapy, prior cancer-related surgery/procedure and prior radiotherapy will be summarized. Best response to prior systemic therapy by lines of therapies and last line as well as by therapy types (e.g., chemotherapy, immunotherapy) will be summarized.

4.8. Subsequent Therapies

The number and percentage of subjects who received subsequent therapy (systemic, cancer-related surgery/procedure and radiotherapy) will be summarized.

5. EFFICACY

5.1. Analysis Specifications

The primary analysis for the Broad Panel Cohort will be conducted approximately 6 months after the first dose administration for the last Broad Panel Cohort subject (reaching approximately 200 response-evaluable subjects) and the analysis will be based on Treated Population in the Broad Panel Cohort. At the time of the primary analysis for the Broad Panel Cohort, an analysis of all other cohorts will also be conducted and will include all subjects with the same enrollment cut-off (the date of the last subject enrollment of Broad Panel Cohort) and clinical cut-off as the Broad Panel Cohort. Additional analyses with longer follow-up may be conducted as needed. The final analysis for the Broad Panel Cohort will be performed at the end of the study (per protocol definition).

The Pediatric Cohort will be analyzed separately for efficacy from the Broad Panel Cohort. The final analysis for the Pediatric Cohort will be performed at the end of the study (per protocol definition). The Pediatric Cohort will have the same primary and secondary endpoints as the Broad Panel Cohort. Analysis may also be conducted by pooling subjects from Broad Panel Cohort and Cholangiocarcinoma Expansion Cohort.

The Exploratory Cohort will be analyzed for efficacy based on the Treated Population of the Exploratory Cohort at the time of primary analysis of the Broad Panel Cohort on ORR assessed by investigator.

The Cholangiocarcinoma Expansion Cohort will be evaluated for efficacy at the time of primary analysis and final analysis of the Broad Panel Cohort. Similar endpoints and analyses as Broad Panel Cohort will be conducted for the Cholangiocarcinoma Expansion Cohort.

5.1.1. Level of Significance

In general, statistical inference on the primary endpoint will be tested at 0.025 one-sided level, unless otherwise specified. All interval estimations will be reported using 2-sided 95% CIs.

Multiplicity adjustment for testing the primary endpoint ORR in both Broad Panel Cohort and Core Panel Cohort is based on an error-spending function approach (Spiessens and Debois, 2010). It uses the correlation between the two test statistics in the Core Panel Cohort and the Broad Panel Cohort. The α level for testing the hypothesis in the Core Panel Cohort will use Hwang-Shih-DeCani error spending function with gamma 0 and the information fraction as the ratio of the observed number of subjects in the Core Panel Cohort over the observed number of subjects in the Broad Panel Cohort at the time of primary analysis.

5.1.2. Data Handling Rules

Unless specified otherwise, missing values will not be imputed. Other data handling rules if any will be outlined in the DPS.

5.1.3. General Analysis Considerations

Descriptive statistics and subject listings will be used to summarize the data. For continuous variables, the number of observations, means, standard deviations, medians, and ranges will be used. For discrete variables, frequency and percentage will be presented. For time-to-event variables, Kaplan-Meier estimates will be provided. In general, all interval estimation will be reported using 2-sided 95% CIs.

5.2. Primary Efficacy Endpoint(s)

5.2.1. ORR assessed by IRC Definition

A subject's best objective response (BOR) is defined as the best objective response a subject achieved during the study in the order of Complete Response (CR), Partial Response (PR), Stable Disease (SD), Progressive Disease (PD), where CR and PR are confirmed as per RECIST v1.1 or RANO. Responders are subjects with BOR of CR or PR. Subjects without measurable disease at baseline or without post-baseline tumor assessment are considered as non-responders.

ORR assessed by IRC is defined as the proportion of responders in an analysis population as assessed by IRC.

For the interim analysis (Interim I, II and III), a subject's BOR may also consider the unconfirmed Complete Response(uCR) and unconfirmed Partial Response(uPR). A subject's response will be classified as unconfirmed CR or PR if only one CR or PR has been observed and a subsequent valid disease evaluation has not been performed yet at the time of the interim analysis. However, a subject will be assigned SD/NE if the subject has only one CR or PR and has no subsequent

disease evaluation and is off study or started subsequent anti-cancer therapy. Two sets of analysis based on different definition of responder will be provided for DRC review for decision making:

- 1) Subjects with unconfirmed response (uCR or uPR) will be considered responders. However, subjects who have initially demonstrated a uCR or uPR but on subsequent evaluation have shown PD will not be considered responders.
- 2) Subjects with unconfirmed response (uCR or uPR) will not be considered as responders.

5.2.2. Estimand

The primary estimand, the main clinical quantity of interest to be estimated in this study, is defined by the following four components (ICH E9 (R1) Addendum, 2018):

- Population: subjects with advanced solid tumors and target FGFR Gene Alterations.
- Variable: subject responder status (responder – BOR of CR or PR; otherwise – non-responder).
- Intercurrent events: treatment discontinuation and subsequent anti-cancer therapy. The treatment policy strategy will be applied to account for the treatment discontinuation. That is, the value for the variable of interest is used regardless of whether the treatment discontinuation occurs. The while-on-treatment policy will be applied to account for subsequent anti-cancer therapy. That is, only the value for the variable of interest before the subsequent anti-cancer therapy will be used. For instance, if a subject discontinued study treatment but did not start subsequent anti-cancer therapy, the subject's responder status/tumor assessment will be used as if the subject is still on treatment regardless of the treatment discontinuation (i.e. the treatment policy). But if a subject started subsequent anti-cancer therapy, no matter whether the subject has discontinued treatment or not, the subject's responder status/tumor assessment after the subsequent anti-cancer therapy will not be used in the analysis (the while-on-treatment policy).
- Population-level summary: ORR assessed by IRC.

5.2.3. Analysis Methods

5.2.3.1. Primary Analysis

Before the primary efficacy test, a final futility assessment using the same futility guideline at the interim analysis (i.e, $\text{Pr}(\text{ORR} > 25\%) < 40\%$) will be conducted for all enrolled tumor histologies to identify the tumor histologies for the pooled primary efficacy analysis. This futility assessment takes into consideration the possibly enrolled new subjects in tumor histologies after Interim III, as well as more available information of the subjects that continue treatment and become evaluable in the early futile tumor histology groups. All available data (eg, efficacy, safety, and biomarker data) will be assessed by the DRC to determine whether a given tumor histology is futile. The primary efficacy analysis after the final futility assessment will be performed on the pooled data from all tumor histologies that didn't meet futility in this final futility assessment for the Treated Population in the Broad Panel Cohort and the Core Panel Cohort.

The null hypothesis of $H_0: ORR \leq 15\%$ will be tested at a significant level of 0.025 using one-sided exact binomial test. The test will be performed on the pooled data of all tumor histologies that didn't meet the futility criteria in the Broad Panel Cohort. An additional test will be performed on the pooled data from all tumor histologies that didn't meet the futility criteria in the Core Panel Cohort as mentioned in Section 0.

The ORR assessed by IRC and its two-sided 95% Clopper-Pearson CI will also be provided.

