Besides the BHM based futility guideline, all available interim data (eg, efficacy, safety, and biomarker data) will be assessed to determine whether enrollment in a given tumor histology should continue, such as the representativeness of biomarker alterations (the expected variant representation by tumor histology based on genomic database assessment). If a tumor histology is deemed futile by the DRC, further enrollment in the histology group will stop; subjects who have been enrolled in the tumor histology group will continue treatment and evaluation as per the protocol. Note that in the primary analysis, a final futility assessment using the same futility guideline as at the interim (i.e, posterior $Pr(ORR > 25\%) < 40\%$) but based on ORR by IRC will be performed for all enrolled tumor histologies as part of the primary analysis to identify the tumor histologies for the pooled primary efficacy analysis (Details in section [5.2.3](#)).

Other details of the planned analysis and efficacy/futility assessment are specified in Section [4-6](#).

Figure 2: Interim Analysis for the Broad Panel Cohort

*At Interim Analysis II, both futility and efficacy will be assessed.

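### SAP 5.2.3.1 lets DRC judgement, made with IRC responses in view, set the primary pool; the simulated false-positive rate covers only the fixed 40% rule

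*SAP*

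**What the plan says.** Before the primary test, SAP 5.2.3.1 places "a final futility assessment using the same futility guideline at the interim analysis", with the threshold Pr(ORR>25%)<40%, to choose the histologies that are pooled. SAP 3.2 describes the same step as "a final futility assessment using the same futility guideline as at the interim" and says of its data: "based on ORR by IRC will be performed for all enrolled tumor histologies as part of the primary analysis".

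Section 5.2.3.1 then describes the decision in two ways. The first gives it to the DRC: "All available data (eg, efficacy, safety, and biomarker data) will be assessed by the DRC to determine whether a given tumor histology is futile". The second, in the paragraph that defines the test, is a rule: "The test will be performed on the pooled data of all tumor histologies that didn't meet the futility criteria in the Broad Panel Cohort". The null hypothesis of ORR at most 15% "will be tested at a significant level of 0.025 using one-sided exact binomial test". The final assessment is also to use "more available information of the subjects that continue treatment and become evaluable in the early futile tumor histology groups".

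The same mix of guideline and judgement appears at the interims: "Besides the BHM based futility guideline, all available interim data (eg, efficacy, safety, and biomarker data) will be assessed". There the consequence is whether enrolment in a histology continues (SAP 3.2, Protocol 9.5).

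Protocol 9.5 and SAP 3.2 define the futility criteria by the 40% threshold. Neither document says that the threshold is binding at the final step, or how safety or biomarker data may override it. Appendix A.2 lists only the fixed threshold among the simulation settings.

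**The concern.** At an interim, judgement affects only whether a histology keeps enrolling. At the final step enrolment is over, and the only consequence is whose responses count in the primary test. The committee would decide this with IRC response counts in view. A histology near the 40% line could be kept or dropped for reasons that the SAP does not specify.

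Two things are at stake. The population of the primary test is not fully fixed in advance, and the same decision feeds the Core Panel test (SAP 5.2.3.1) and the Japan analyses (Appendix A.4). Also, the operating characteristics in Appendix A.3 belong to a fixed rule, so they need not describe the procedure as worded. This is separate from the inflation caused by applying a fixed rule to the same responses that are then tested, which Appendix A.3.3 already reports.

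**Working it through.** **Inputs.**
- Null ORR 15%, one-sided exact binomial test at 0.025 (SAP 1.3, 5.2.3.1).
- 200 response-evaluable subjects, cap 30 per histology, interims at 60, 100 and 140 with 6 weeks to endpoint, at least 5 subjects for an interim stop, futility if Pr(ORR>25%)<40%, no dropout (Appendix A.2).
- Priors from Appendix A.1: mu ~ N(-2.19, 2²); inverse gamma for tau², weight 0.75, read as centred at tau = 2.
- Prevalences from Table A1: 18, 18, 13, 13, 10, 5, 4, 4, 3, 2, 2, 1, 1, 1 and Other 5 (%).
- Accrual: Poisson, peak 5 per week. The ramp is in a figure that is not shown; 4 weeks was assumed.

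**Method.** There is no closed form, so 20,000 trials were simulated under Global Null. For histology g with n_g subjects and x_g responders, the hierarchical model gives p_g = Pr(ORR_g > 25% | data). The pool S holds the histologies kept. With N = sum of n_g and X = sum of x_g over S, a trial is a false positive if Pr(Binomial(N, 0.15) ≥ X) ≤ 0.025.

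**Step 1: reproduce the SAP figure.** With a fixed rule, early-stopped histologies left out and groups under 5 never called futile, the rate is 18.64%, against 18.57% in Appendix A.3.3. The Monte Carlo standard error is √(0.1864 × 0.8136 / 20,000) ≈ 0.28 points. Side checks, re-simulated against SAP:
- duration 252 and 251 weeks;
- false positives that include a group under 5 subjects, 37.6% and 36.7%;
- false positives that include Other, 17.4% and 16.34%;
- Target power 96.9% and 97.63%.

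One figure does not match. This reading gives 76.8% probability of selecting at least 12 of 15 under Alternative, against about 83% in A.3.3. Re-assessing early-stopped histologies and small groups gives 84.0%, but then the false-positive rate is 24.17%. No single reading tried matched both figures.

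**Step 2: vary the final step.** The override patterns are assumptions; the documents describe none of them.

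| Final step | Global Null false-positive rate |
|---|---|
| Fixed rule, early-stopped out, n<5 never futile | 18.64% |
| Fixed rule, early-stopped out, n<5 assessed | 19.30% |
| Fixed rule, early-stopped may re-enter, n<5 never futile | 23.41% |
| Fixed rule, early-stopped may re-enter, n<5 assessed | 24.17% |
| First row, one histology switched, least favourable | 2.6% |
| First row, one histology switched, most favourable | 29.2% |
| 10% of decisions reversed at random | about 12% |
| Best-looking subset chosen freely | 48.7% |
| No histology excluded | 2.0% |

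For the one-switch rows, a single change can create a success in 10.56% of null trials and remove one in 16.01%: 18.64 + 10.56 ≈ 29.2, and 18.64 − 16.01 ≈ 2.6.

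**The case against.** The strongest reply is that the SAP already has a rule. Protocol 9.5 and SAP 3.2 define the futility criteria numerically, the sentence that defines the test pools histologies by those criteria, and SAP 3.2 describes the final step without mentioning the DRC. If the DRC follows the guideline, 18.57% applies under the simulation's own assumptions. All of this stands. A reader might infer that the primary analysis set is wholly discretionary, or that the SAP's false-positive rate is void; the documents support neither.

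A reader might also infer that judgement inflates the error, with 48.7% as the likely size. That does not follow. One changed histology can lower the rate as well as raise it, and random reversals lower it. The 48.7% needs a committee that picks the best-looking subset, which nothing in the documents describes; the example of judgement in SAP 3.2 is how representative the biomarker alterations are. It is an adversarial ceiling.

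SAP 5.2.3.2 also commits to an analysis with all histologies, including those deemed futile, and to each histology's posterior probability. Departures from the rule would therefore be visible. Because these analyses are supplementary, they mitigate the problem but do not control the primary test. Finally, DRC procedures are left to a charter that is not among the documents and may restrict this step.

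The reply does not remove the sentence that assigns the decision to the DRC on data of any kind, and nothing in the protocol or SAP subordinates that sentence to the rule.

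**Conclusion.** The concern holds as an unreconciled passage with consequences for the primary test. The SAP allows committee judgement, informed by the primary endpoint, to set the tested population, and does not make the 40% rule binding. The 18.57% is neither an estimate nor an upper bound for the procedure as worded. It is not shown to be too low either. The 2.6% to 29.2% range rests on assuming that exactly one histology's status is changed, and on the ramp and prior readings listed above. Part of the ambiguity does not depend on judgement at all: whether early-stopped histologies can re-enter by the same fixed rule moves the rate from about 19% to about 23–24%.

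**What to change.** In SAP 5.2.3.1:

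1. Make the rule binding for the primary pool: a histology is included if and only if the model's Pr(ORR>25%), computed on IRC response, is at least 40%. Delete the sentence giving the decision to the DRC at this step.
2. State whether histologies stopped early for futility can re-enter, and how groups with fewer than 5 subjects are treated.
3. Re-run the Appendix A.3 simulation for the rule as finally worded, and report its false-positive rate and selection power.
4. Put any DRC-judged pool in a labelled supplementary analysis.

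The protocol's Amendment 5 history describes the adult primary analysis as complete. If the pool has already been set, report the rule-based pool beside the pool used and list every departure.

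The cost is SAP wording and a simulation re-run, with no new data. Judgement over borderline histologies in the primary test is given up, and the stated false-positive rate may become less favourable, for instance if re-entry is allowed. Safety concerns about a histology can still be reported separately. The change does not remove the inflation from selecting and testing on the same responses; Appendix A.3.3 discloses that, and Table A5 shows the effect of lower alpha levels.

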For the Broad Panel Cohort, the primary endpoint is ORR based on RECIST v1.1. or RANO as assessed by the IRC and will be calculated with a 95% 2-sided exact confidence interval (CI). The primary endpoint will be analyzed using data from the Treated Population (defined as all subjects [FGFR+] who receive at least 1 dose of study drug) in the Broad Panel Cohort and the Core Panel Cohort. An error-spending function approach will be used to split the significance level for the Broad Panel Cohort and the Core Panel Cohort. The secondary endpoints include ORR by investigator assessment, DOR, DCR, CBR, PFS, OS, PK exposure parameters, incidence and severity of AEs, and PROs. The ORR assessed by the investigator will be analyzed in the same way as the ORR assessed by the IRC. The distributions of DOR, PFS and OS will be summarized using Kaplan-Meier estimates and the estimated median will also be reported along with a 95% CI. The PRO assessments will be analyzed with descriptive summaries (ie, mean, standard deviation including change from baseline) at each assessment time point. The Pediatric Cohort will have the same primary and secondary endpoints as the Broad Panel Cohort; subjects in the Pediatric Cohort will also be evaluated separately from the Broad Panel Cohort. The Cholangiocarcinoma Expansion Cohort will also be evaluated separately from the Broad Panel Cohort.

Three interim futility analyses are planned when 30%, 50%, and 70% of the subjects in the Broad Panel Cohort (ie, approximately 60, 100, and 140 subjects) have been treated and are considered responseevaluable by investigator assessment, irrespective of the tumor histologies and the distribution among the tumor histologies. The interim analyses for futility will be based on the ORR assessed by investigator using a Bayesian hierarchical model (BHM), implemented in FACTS v6.2 Enrichment Design – Dichotomous. In addition, an interim efficacy analysis will be conducted for the Broad Panel Cohort at the same time as the second interim futility analysis.

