9.4.3. Efficacy Analyses

9.4.3.1. Primary Analysis

The primary analysis for the Broad Panel Cohort will be conducted approximately 6 months after the first dose of the last Broad Panel Cohort subject (reaching approximately 200 response-evaluable subjects) and the analysis will be based on Treated Population in the Broad Panel Cohort.

The primary efficacy analysis will be performed on the pooled data of all tumor histologies that did not meet the futility for the Treated Population in the Broad Panel Cohort and the Core Panel Cohort. The primary endpoint ORR (CR or PR) according to RECIST v1.1 or RANO criteria assessed by the IRC will be calculated with 95% 2-sided exact CI. Statistical inference on ORR by IRC will be tested at 0.025 one-sided level, unless otherwise specified. To adjust for multiplicity, an error-spending function approach (Spiessens 2010) will be used to split the significance level using the observed size of the Core Panel Cohort relative to the size of the Broad Panel Cohort.

Refer to the SAP for details of the supplementary and sensitivity analyses.

Other efficacy analyses that will be focused on the Broad Panel Cohort and the Core Panel Cohort include:

- ORR (CR or PR) according to RECIST v1.1 or RANO criteria assessed by the investigator will be calculated with 95% 2-sided exact CI
- The distributions of DOR will be summarized using Kaplan-Meier estimates based on responding subjects. The estimated median will also be reported along with a 95% CI
- DCR and CBR will be calculated with 95% 2-sided exact CI
- PFS and OS will be summarized using similar Kaplan-Meier methods

Safety and efficacy analyses will be conducted on the Cholangiocarcinoma Expansion Cohort and the Exploratory Cohort at the same time as the primary analysis of the Broad Panel Cohort.

Primary Analysis for the Pediatric Cohort

The treated subjects (approximately 20) who have either progressed following prior therapies and who have no acceptable standard therapies in the proposed Pediatric Cohort (including the adolescent subjects enrolled in the Broad Panel Cohort) will be the primary analysis population for the Pediatric Cohort. The additional approximately 6 subjects who have a newly diagnosed solid tumors and who have no acceptable standard therapies will be analyzed separately from the Broad Panel Cohort.

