APPENDIX

The appendix includes details about the BHM, simulation assumptions and design setups, operating characteristics for Broad Panel Cohort only and with multiplicity adjustment for Core Panel Cohort.

A.1. Bayesian Hierarchical Model (BHM)

Denote $\pi_g = \Pr(\text{response}|\text{treatment}, g)$, the BHM models the log-odds of response (i.e. ORR) defined as

$$\theta_g = \text{logit}(\pi_g) = \ln\left(\frac{\pi_g}{1 - \pi_g}\right)$$

with weak priors

$$\begin{aligned}\theta_g &\sim N(\mu, \tau^2) \\ \mu &\sim N(-2.19, 2^2)\end{aligned}$$

$\tau^2 \sim \text{Inverse Gamma distribution with mean 2 and weight 0.75.}$

The prior normal mean value of -2.19 for μ corresponds to the logit of 10%. The prior distribution of μ is shown in [Figure A1a](#), and it corresponds to a log odds range of 0% to 99.7%. The parameter τ represents the degree of heterogeneity between the tumor histology groups, thus the degree of borrowing. At one extreme, when τ is 0, there is complete borrowing. At the other extreme, when τ is near infinity, there is no borrowing across the groups. For values between these two extremes, there is an amount of borrowing consistent with the variability across groups. The mean for τ is set to the same value as the prior standard deviation for μ , and the weight is set to be 0.75. The distribution of τ is shown in [Figure A1b](#). It is to ensure certain degree of borrowing.

[figure not shown]

Figure A1: Prior Distribution of Hyperparameters of BHM. a) Prior Distribution of μ . b) Prior Distribution of τ

A.2. Simulation Assumptions and Setups

The simulation study in this section is based on the Broad Panel Cohort which enrolls patients with target FGFR mutations or any gene fusion, considering three protocol specific interim futility analyses and the primary analysis. Note that there will be an efficacy assessment at the second

interim, but it is not considered in the simulation for its ignorable impact with a use of an alpha of < 0.01% in the proposed early success rule. The simulation study has the following assumptions and parameter setups.

Assumptions on Prevalence

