Note that the futility threshold 40% and the success threshold 80% were justified through extensive simulations to achieve good balance of design operating characteristics under various scenarios.

A.3. Operating Characteristics

The following simulations results are based on the Broad Panel Cohort only with no multiplicity adjustment. All scenarios were conducted using the FACTS v6.2 Enrichment Design – Dichotomous engine and the results from FACTS are post-processed in R.

A.3.1. Scenarios

As mentioned in section A.2., 14 tumor histologies and one Other group were assumed for enrollment. Below we use the shorthands: GBM (glioblastoma), Lung (squamous non-small cell lung cancer), HN (squamous cell head and neck cancers), Gastric (gastric cancer), Breast (breast cancer), Cholangio (Cholangiocarcinoma), Endometrial (endometrial cancer), Glioma (glioma), Ovarian (ovarian cancer), and STS (soft tissue sarcoma), RCC (renal cell cancer), Cervical (cervical cancer), Esophageal (Esophageal cancer), and Hepatocellular (hepatocellular cancer). Table A2 lists the simulation scenarios. The percentage number under each tumor histology is the proportion of the tumor histology in the trial assumed for enrollment (see Table A1 for details). The scenarios are based on the assumed true ORR for each tumor histology. Six scenarios are shown, with different true ORRs for each histology and the group Other. The last column of Table A2 shows the (prevalence) weighted average ORR as the overall truth assumed on the original tumor agnostic pool (the Broad Panel Cohort before possible futility on any tumor histologies).

More specifically, the simulation scenarios include:

- **Global Null:** the true ORRs for all tumor histologies and the group Other are 15% at the boundary of the null hypothesis (i.e., $\text{ORR} \leq 15\%$). Under this scenario, all tumor histologies and the original tumor agnostic pool are nonactive and should not succeed as a pool after futility analysis at the primary efficacy analysis.
- **Alternative:** the true ORRs for all tumor histologies and the group Other are 35%, at the boundary of the alternative hypothesis (i.e., $\text{ORR} \geq 35\%$). Under this scenario, all tumor

histologies and the original tumor agnostic pool are active and expected to succeed as a pool after futility analysis at the primary analysis.

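### SAP 5.2.3.1 gives the Broad Panel test the full one-sided 0.025, while the protocol splits that level with the Core Panel; the reduced Broad Panel level is written nowhere

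*SAP*

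**What the plan says.** **Protocol.** The Synopsis says an error-spending approach "will be used to split the significance level for the Broad Panel Cohort and the Core Panel Cohort". Protocol 9.4.3.1 sets a one-sided 0.025 and says the approach "will be used to split the significance level using the observed size of the Core Panel Cohort" relative to the Broad Panel. The hypothesis (9.1) is an ORR of at most 15% against 35%, and success may be claimed in either cohort or in both.

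**SAP 5.1.1** adopts a multiplicity adjustment for the two cohorts. On the method: "It uses the correlation between the two test statistics in the Core Panel Cohort and the Broad Panel Cohort". It then gives one cohort a rule: "The α level for testing the hypothesis in the Core Panel Cohort will use Hwang-Shih-DeCani error spending function with gamma 0", with the observed Core/Broad ratio as information fraction. It gives no rule for the Broad Panel.

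**SAP 5.2.3.1**, which defines the test, says the null hypothesis "will be tested at a significant level of 0.025 using one-sided exact binomial test" and names the pooled Broad Panel. It adds a further test on histologies that did not "meet the futility criteria in the Core Panel Cohort as mentioned in Section 0". The SAP has no Section 0.

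**SAP Appendix.** The opening announces "operating characteristics for Broad Panel Cohort only and with multiplicity adjustment for Core Panel Cohort". Section A.3 then states: "The following simulations results are based on the Broad Panel Cohort only with no multiplicity adjustment". The contents list shows no other section with adjusted results. A.4 (Japan) drops Core Panel inference, so it does not supply the Broad level either.

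**The concern.** With two routes to success, the Broad and Core levels together must use up 0.025 and no more. The correlation in 5.1.1 has only one use, which is to derive a Broad level below 0.025 once the Core level is fixed, so a split was evidently intended. Yet the section a programmer would implement gives the Broad Panel the whole 0.025 and still tests the Core Panel.

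Two thresholds can therefore be defended from the approved texts, and they disagree on a borderline result. The choice must be fixed before the data are seen.

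**Working it through.** **Inputs.** Overall one-sided α = 0.025 and null ORR 15% (Protocol 9.1 and 9.4.3.1). Exact binomial test (SAP 5.2.3.1). Core rule: Hwang-Shih-DeCani with gamma 0 (SAP 5.1.1). Broad Panel: 200 response-evaluable, about 240 enrolled (Protocol 9.2). Assumed, because the documents do not give it: t = Core/Broad from 0.1 to 0.9, with the Core pool nested in the Broad pool.

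**The plan's own figures first.** Table A5 at level 0.025 gives power 1 (Alternative) and 0.9763 (Target), for the Broad Panel alone. A rebuild of the SAP A.1 and A.2 design, with an assumed 20-week accrual ramp, gave 1.000 and 0.970. Its probability of selecting at least 12 of 15 histologies was 82.5%, against a stated figure of about 83%. The Global Null false positive rate was not reproduced (0.223 against 0.1857), possibly because of software settings that are not reported. Nothing below uses it.

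**Step 1, Core level.** The spending function is α(1 − e^(−γt))/(1 − e^(−γ)). As γ → 0 it becomes αt, so α_core = 0.025t.

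**Step 2, correlation.** For nested counts, Cov(X_core, X_broad) = Var(X_core), so ρ = √t.

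**Step 3, error if 5.2.3.1 is followed literally.** This is 1 − Φ₂(z at 0.025, z at 0.025t; ρ = √t).

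**Step 4, Broad level under the split.** α_broad solves 1 − Φ₂(z at α_broad, z at 0.025t; √t) = 0.025.

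| t | α_core | Either-test error, literal | α_broad under split |
|---|---|---|---|
| 0.1 | 0.0025 | 0.0271 | 0.0229 |
| 0.2 | 0.0050 | 0.0288 | 0.0210 |
| 0.3 | 0.0075 | 0.0303 | 0.0194 |
| 0.4 | 0.0100 | 0.0314 | 0.0180 |
| 0.5 | 0.0125 | 0.0322 | 0.0168 |
| 0.6 | 0.0150 | 0.0326 | 0.0157 |
| 0.7 | 0.0175 | 0.0327 | 0.0149 |
| 0.8 | 0.0200 | 0.0322 | 0.0143 |
| 0.9 | 0.0225 | 0.0309 | 0.0145 |

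**Step 5, the verdict at the margin.** Exact tails at ORR 15%:

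- N = 200: P(X ≥ 41) = 0.0220 and P(X ≥ 42) = 0.0140. The critical count is 41 at level 0.025. Under the split it is 42 for t = 0.2 to 0.9, and unchanged at t = 0.1.
- N = 240: P(X ≥ 48) = 0.0218, P(X ≥ 49) = 0.0144 and P(X ≥ 50) = 0.0093. The critical count is 48 at level 0.025. Under the split it is 49 for t = 0.2 to 0.9, except 50 at t = 0.8, and unchanged at t = 0.1.

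**Step 6, exact either-test error.** The Core count is round(N × t). Both tests are exact, and the probability that either rejects is summed over the Core responders.

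- Literal reading, N = 200: 0.0231 to 0.0288, above 0.025 at 8 of 9 values of t.
- Literal reading, N = 240: 0.0230 to 0.0289, above 0.025 at 6 of 9.
- Literal reading, all N from 150 to 240 (91 sizes × 9 values of t = 819 cases): 0.016 to 0.031, above 0.025 in 356.
- Under the split, same 819 cases: maximum 0.0246.

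**Step 7, which correlation.** 5.1.1 takes t from cohort sizes, but 5.2.3.1 tests the pools left after futile histologies are removed. At t = 0.5, α_core = 0.0125 and ρ = √0.5 gives α_broad = 0.0168. If the tested pools have ratio 0.3, that pair has nominal error 0.0267, and α_broad should be 0.0148. If their ratio is 0.7, the error is 0.0228, and α_broad can be 0.0195.

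**The case against.** The strongest reply is that the SAP already adopts the split. Section 5.1.1 sets 0.025 only as a default, then specifies the method, spending function, gamma, information fraction and use of the correlation. With overall α of 0.025 these determine the Broad level once t is observed, and no number could be written earlier. On that view, the 0.025 in 5.2.3.1 is the overall level, and Section 0 is a failed cross-reference field like others in the SAP's Figure 1 notes. This explains the probable intent, and the bad pointer is indeed an editorial fault. It does not settle the rule: 5.2.3.1 ties 0.025 to the Broad Panel test itself, and the derivation is written nowhere.

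The second reply is that little turns on it, and most of this stands. At N = 200, for t = 0.2 to 0.9, the readings differ only at exactly 41 responders. The probability of that count is 0.8% at true ORR 15%, 6.9% at 20%, 2.3% at 25% and about 0.0003% at 35%. The Broad critical count is the same under both rules in 208 of the 819 cases, and the literal rule stays within 0.025 in 463. The final tested N is also unknown, so 41/200 and 48/240 are illustrations and not planned thresholds.

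Third, futility selection inflates the error far more: the SAP reports 18.57% under the Global Null for the Broad Panel alone. That is true, and the repair here does not address it.

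Finally, taking the correlation from the tested pools goes beyond what 5.1.1 says. It does, but without it the intended method misses 0.025 whenever exclusions change the overlap.

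**Conclusion.** The concern holds. SAP 5.2.3.1 contradicts the protocol and sits badly with SAP 5.1.1, and neither document states the Broad Panel level under the split. It should be fixed, although the numerical effect is modest. The literal reading has a nominal either-test error of at most 0.0327 and an exact error of at most 0.031, above 0.025 in 356 of 819 cases. At N = 200 or 240 the critical count usually differs by one responder. The case for acting is that the verdict on a borderline result depends on which section is followed.

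These figures assume ORR 15% throughout, nested pools, t from 0.1 to 0.9 and no futility selection.

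**What to change.** In SAP 5.2.3.1, replace 0.025 for the Broad Panel with α_broad, defined as the value for which the null probability of rejecting Core at 0.025t or Broad at α_broad equals 0.025. Point the Core test to Section 5.1.1. Keep the cohort-size ratio in 5.1.1 as the spending fraction t, and state that the correlation used to solve for α_broad comes from the overlap of the two pools actually tested. Either add the adjusted operating characteristics that the Appendix announces or delete the announcement.

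**Cost.** One or two sentences for the rule itself. The Broad critical count rises as in Step 5. At N = 200, moving from 41 to 42 leaves power above 99.99% at a true ORR of 35%; at 25%, in a fixed pool of 200, it falls from 94.2% to 92.0%. At N = 240, moving from 48 to 49 takes power at 25% from 97.1% to 95.9%. Table A5 points the same way: at levels 0.02 and 0.015, power stays at 1 under Alternative and is 0.9721 and 0.9678 under Target, against 0.9763 at 0.025.
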